#### 9.6.2. Record Retention

To enable evaluations and/or inspections/audits from regulatory authorities or Pfizer, McKesson agrees to keep all study-related records, including the identity of all participating patients (sufficient information to link records, eg, CRFs and hospital records), copies of all CRFs, safety reporting forms, source documents, detailed records of treatment disposition, and adequate documentation of relevant correspondence (eg, letters, meeting minutes, and telephone call reports). The records should be retained by McKesson according to local regulations or as specified in the research agreement, whichever is longer. McKesson must ensure that the records continue to be stored securely for so long as they are retained.

If McKesson becomes unable for any reason to continue to retain study records for the required period, Pfizer should be prospectively notified. The study records must be transferred to a designee acceptable to Pfizer.

Study records must be kept for a minimum of 15 years after completion or discontinuation of the study, unless McKesson and Pfizer have expressly agreed to a different period of retention via a separate written agreement. Record must be retained for longer than 15 years if required by applicable local regulations.

McKesson must obtain Pfizer's written permission before disposing of any records, even if retention requirements have been met.

# 9.7. Data Analysis

Detailed methodology for summary and statistical analyses of the data collected in this study are outlined here and further detailed in a statistical analysis plan (SAP), which will be maintained by the sponsor. The SAP may modify what is outlined in the protocol where appropriate; however, any major modifications of the primary endpoint definitions or their analyses will also be reflected in a protocol amendment.

## 9.7.1. Statistical Hypotheses

The primary purpose of this study is to estimate real world tumor response for pre/peri-menopausal patients treated with palbociclib + AI or AI alone as first line treatment for HR+/HER2- MBC in the US clinical practice setting. No formal hypothesis testing will be performed.

## 9.7.2. Sample Size Determination

Approximately 385 patients will be included with close to a 1:2 ratio between palbociclib + AI and AI alone cohorts based on examination of structured iKM data applying inclusion/exclusion criteria (Table 2 and Table 3) between 01 January 2010 and 30 June 2020. It is estimated that there will be approximately 135 patients in the palbociclib + AI arm and 250 patients in the AI alone arm of which a subset will have documented post-baseline tumor assessment.

#### 9.7.3. Cohort for Analysis

All effectiveness analyses will be based on the pre/perimenopausal cohort. Eligible pre/perimenopausal patients with HR+/HER2- MBC will be included into the following cohorts:

**Cohort** to be analyzed for the primary objective:

- a. Pre/perimenopausal patients treated with palbociclib + an AI as the initial therapy for the treatment of MBC.
- b. Pre/perimenopausal patients treated with an AI alone as the initial therapy for the treatment of MBC.

## 9.7.3.1. Propensity Score Matching (PSM)

Propensity score matching (PSM) will be used to create matched sets of palbociclib treated and untreated patients who shared similar value of the propensity score. The propensity scores produce a set of matched pairs with similar distributions of the covariates but does not require close or exact matches for each individual matched pair of patients. Once the matched sample has been formed, the treatment effect can be estimated by directly

comparing outcomes between palbociclib treated and untreated patients in the matched sample. Variables to be used in the estimation of propensity scores (PS) may include key baseline demographics (ie, age, race) and clinical characteristics (Eastern Cooperative Oncology Group [ECOG] performance score, disease stage at initial diagnosis, visceral metastasis, Charlson Comorbidity Index, and number of disease sites). A final list will be specified in the SAP.

## 9.7.3.2. Analyses of Primary Endpoint

The primary endpoint is real-world response rate (rwRR) and the rwRR will be calculated as the proportion of patients with a real-world complete response (CR) or real-world partial response (PR) by treatment cohort. Patients with a best response of CR or PR are those patients with a CR or PR after 30 days of treatment initiation without a PD at any prior assessment.

Real-world tumor responses (rwTR) are assessed based on treating clinician's assessment of radiological evidence for change in burden of disease over the course of treatment. Assessments were not performed on a schedule and responses were not confirmed by subsequent assessment. Each assessment will be classified as follows:

- Complete response (CR): Documented as "a complete response" to therapy; indication patient is in "remission"; "all lesions" have disappeared or "no evidence of disease").
- Partial response (PR): Documented as partial reduction in size of visible disease in some or all areas without any areas of increase in visible disease (decrease in disease volume even though disease is still present).
- **Stable disease (SD):** Documented as disease is stable (not progressed or not improved; eg, stable appearance of lobe nodules) or Mixed response, which is a combination of improved and worsened disease.
- **Progressive disease (PD):** Documented as disease has "progressed"; or worsening of disease.
- Not evaluated (NE): No documentation of status of disease.

To overcome the potential imbalance of baseline characteristics between the 2 cohorts, the propensity score (PS) will be computed by a logistic regression model using baseline characteristics for each patient. The PSM technique will be used to control for potential confounding factors when comparing the cohorts. Each patient in the palbociclib + AI cohort will be matched (1:1) to a patient in the AI alone cohort using a greedy matching algorithm, which sequentially without replacement selects the control patient whose propensity score is closest to that of the particular patient in the palbociclib + AI cohort. This matching process will be performed independently and prior to the access of rwTR outcome data.

The analysis of the primary endpoint is to estimate the rwRR between the 2 cohorts (palbociclib + AI compared to AI alone) using PSM method to balance baseline demographic and clinical characteristics between the two real world treatment cohorts.

The number and percentage of patients with a best overall response of CR, PR, SD, PD, and NE will be tabulated. The number and proportion of patients achieving rwTR (CR or PR) will be summarized along with the corresponding exact 2-sided 95% confidence interval calculated using a method based on Clopper-Pearson method. The odds ratio and the corresponding 2-sided 95% confidence interval will be calculated to contrast the treatment effectiveness on response rates.

Two analyses of rwRR will be performed:

- 1. rwRR among those patients who had at least one post-baseline tumor assessment documented in the database.
- 2. rwRR among all eligible patients who met the inclusion and exclusion criteria as defined in study protocol.

The rwRR rates will be estimated for each treatment cohort and compared by using PSM methodology to control potential baseline confounding factors.

## 9.7.3.3. Sensitivity Analyses

Sensitivity analysis will be performed to exam the robustness of the primary analysis.

## Sensitivity analysis 1: Inverse probability treatment weighting (IPTW)

Inverse probability treatment weighting will be used to balance baseline demographic and clinical characteristics between comparison cohorts in this analyses (Austin and Stuart, 2015). In the event that IPTW method does not balance potential confounder variables, analysis by PS quintiles will be used.

## Sensitivity analysis 2: **Stratification by propensity score**

This analysis will divide patients into 5 equal-sized groups using quintiles of the estimated propensity score. The treatment effect of rwRR can be estimated by comparing rwRR rates directly between patients in two cohorts within strata. The stratum-specific estimates of treatment effect can then be pooled across stratum to estimate an overall treatment effect.

## Sensitivity analysis 3: Best tumor response imputation

For patients who did not have any post baseline tumor assessment information, their rwTR may be imputed using logistic regression predictive modelling to predict response for patients with similar baseline characteristics from known patients.

## 9.7.3.4. Subgroup Analyses

While inclusion of patients between 2010 and 2015, allows for patient to be included in the control arm prior to palbociclib being approved, which may help to reduce bias in physician choice of treatment and allow for more patients being matched, however, the varying time periods between cohorts may be a limitation.

A subgroup analyses will be performed including patients only after palbociclib approval in the US. Patients included in this analysis with be those who meet inclusion and exclusion criteria during an index period on and after 01 February 2015 until on or before 30 June 2020.

Other subgroup analyses may be performed according to patient demographics and baseline characteristics as appropriate, based on availability of the data and sample sizes.

## 9.7.3.5. Other Analyses

Descriptive analyses for patient baseline characteristics will be conducted.

## 9.7.3.6. Analyses of AEs of Special Interest

The number of cases of pneumonitis and interstitial lung disease (ILD) which are directly attributable to the treatment will be reported for each treatment cohort which occurred while on first line treatment plus 30 days.

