Quality control and validation of chart review (unstructured) data will occur in multiple phases. Chart review processes require that no interpretations be made during the data collection; instead, all data will be collected as documented by the physician in the chart. Prior to full chart review, a pilot will be conducted with at least 5% of the patient population, up to 25 patients. Charts will be reviewed by each reviewer on the team to ensure inter-rater reliability. Data Quality Specialists will review pilot data for accuracy and consistency, including implausible dates (ie, date of death prior to last date of treatment), non-standard treatments, results which are inconsistent with known clinical parameters or other clinical data which is inconsistent with known standards and outcomes. Chart review team will meet following pilot and before launch of full chart review to clarify ambiguous or conflicting data and address potential problems and questions. Pilot data will be presented to the research team for review and approval. If necessary, revisions to the tool and/or additional training will be implemented.

Once the pilot chart review is complete, the remaining chart reviews will proceed. During this phase of chart review, Data Quality Specialists will perform random and detailed checks of the data by verifying original source data. The Data Quality Specialist will also initiate queries, quality control of randomly selected charts and review of final data set before submission to researcher. Finally, the researcher and study's Biostatistician will provide a final examination of the final dataset by looking for missing or illogical data before preparing

it for analyses. This analysis will include a descriptive analysis of the provider characteristics, demographics, baseline clinical and disease characteristics, and characteristics of treatment patterns. Data points flagged as outliers will be reviewed by the Data Quality Specialist.

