#### **Human Review of Unstructured Data**

This study protocol requires human review of patient-level unstructured data; unstructured data refer to verbatim medical data, including text-based descriptions and visual depictions of medical information, such as medical records, images of physician notes, neurological scans, X-rays, or narrative fields in a database. The reviewer is obligated to report adverse events (AEs) with explicit attribution to any Pfizer drug that appear in the reviewed information (defined per the patient population and study period specified in the protocol). Explicit attribution is not inferred by a temporal relationship between drug administration and an AE but must be based on a definite statement of causality by a healthcare provider linking drug administration to the AE.

The requirements for reporting safety events on the non-interventional study (NIS) Adverse Event Monitoring (AEM) Report Form to Pfizer Safety are as follows:

- All serious and non-serious AEs with explicit attribution to any Pfizer drug that appear in the reviewed information must be recorded and reported, within 24 hours of awareness, to Pfizer Safety using the NIS AEM Report Form.
- Scenarios involving drug exposure, including exposure during pregnancy, exposure during breast feeding, medication error, overdose, misuse, extravasation, lack of efficacy, and occupational exposure associated with the use of a Pfizer product must be reported, within 24 hours of awareness, to Pfizer Safety using the NIS AEM Report Form.

For these AEs with an explicit attribution or scenarios involving exposure to a Pfizer product, the safety information identified in the unstructured data reviewed is captured in the Event Narrative section of the report form, and constitutes all clinical information known regarding these AEs. No follow-up on related AEs will be conducted.

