5. ANALYSIS SETS/POPULATIONS

It was projected that approximately 300 patients would be included with close to a 1:1 ratio between palbociclib plus AI and AI monotherapy cohorts based on examination of structured iKM data applying inclusion/exclusion criteria between 01 January 2010 and 30 June 2020. The actual total number of eligible patients is 196 post-chart review. Among the 196 patients, 116 were treated with palbociclib plus AI, 80 were treated with AI monotherapy as first-line treatment for HR-positive, HER2-negative MBC.

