6.2. Safety Endpoints

The number of cases of pneumonitis and ILD which are directly attributable to the treatment which occurred while on first line treatment plus 30 days will be reported for each treatment cohort.

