CCI (Charlson Co-morbidity Index) score	Chart review	Prior medical history	
Calculated based on the presence of 17 Charlson comorbidities at MBC diagnosis.
 
Comorbidities and associated obfuscated dates documented prior to or on the index date will be captured and summarized as:
 
Myocardial infarction, congestive heart failure, peripheral vascular disease, cerebrovascular disease, hemiplegia or paraplegia, chronic pulmonary disease, peptic ulcer disease, diabetes with chronic complications, diabetes without chronic complications, renal disease, rheumatologic disease, dementia, mild liver disease, moderate or severe liver disease, any malignancy including leukemia and lymphoma, metastatic solid tumor, HIV/AIDS.
 
In addition, history of interstitial lung disease (ILD) and pneumonitis will be noted but not included in the CCI score.
 
Two approaches will be used to capture comorbidities documented in patients' medical records. First, comorbidities explicitly documented by providers will be captured and reported. Separately, patients with suspected comorbidities based on receipt of medications associated with those conditions will be identified.
 
To identify suspected comorbidities, an extract of all concomitant meds documented pre-index for the study population cohorts will be generated with patients' entire treatment history documented in the structured data. The study team, including clinical experts and the Physician Investigator, will review the frequency distributions of the medications and map these to chronic conditions.
 
For analysis purposes, comorbidities explicitly documented by providers versus those imputed by medication use will be differentiated.

Disease histology	iKM structured data	Prior medical history	Categorized as: Ductal Lobular Mixed Metaplastic Tubular Mucinous Other No information
BRCA 1/2 status	iKM structured data + chart review	Prior medical history	Categorized as: Positive Negative No information
ESR1 status	iKM structured data + chart review	Prior medical history	Categorized as: Positive Negative

Table 2. Study A5481159 Key Variables

Variable	Source(s)	Period of Measurement	Operational Definition
			No information
NGS status	iKM structured data + chart review	Prior medical history	Categorized as: Positive Negative No information
Treatment characteristics			

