Death date	iKM structured data + LADMF/NDI + chart review	Study observation period	Obfuscated date of death will be captured from the LADMF, NDI as well as iKM. If dates conflict between the 3 sources, the NDI, followed by the LADMF date will be prioritized. If severe data discordance is observed (i.e., death is reported to occur prior to the index date and/or there is a difference of more than 6 months between them), then the iKM death date, as verified through chart review, will be used.
Pneumonitis and interstitial lung disease	Chart review	Study observations period	Explicit attribution to treatment within chart will be documented. Yes/No

Source: Study A5481159 protocol section 9.3 Table 1.

Document Approval Record

Document Name:

Oct 2021 SAP RWE A5481159 Non-Interventional Study Statistical Analysis Plan v1.0

Document Title:

Oct 2021 SAP RWE A5481159 Non-Interventional Study Statistical Analysis Plan v1.0

Signed By:

PPD

Date(GMT)

04-Oct-2021 15:32:37

Signing Capacity

Final Approval

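### Pneumonitis/ILD is counted by cohort only where the chart attributes it to treatment, so the counts mix attribution practice with incidence; all documented cases should be shown as well

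*Protocol*

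**What the plan says.** Protocol 9.7.3.6 limits the safety result to pneumonitis and ILD cases "which are directly attributable to the treatment will be reported for each treatment cohort", occurring on first-line treatment or within 30 days after it. SAP 6.2 sets the same endpoint, "The number of cases of pneumonitis and ILD which are directly attributable to the treatment", and lists no other safety endpoint. SAP 5.2 makes the full analysis set the safety set.

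The operational definition is in the key-variable tables (Protocol Table 1, SAP Table 2): "Explicit attribution to treatment within chart will be documented. Yes/No". Chart reviewers may not interpret. Under Protocol 9.8, "all data will be collected as documented by the physician in the chart".

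Protocol 11 uses the same term for the 24-hour safety reports to the sponsor and defines it there: "Explicit attribution is not inferred by a temporal relationship between drug administration and an AE"; it "must be based on a definite statement of causality by a healthcare provider linking drug administration to the AE".

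Two related items are collected but have no role in this endpoint. In the comorbidity variable, "history of interstitial lung disease (ILD) and pneumonitis will be noted but not included in the CCI score". Prior and concomitant radiotherapy are also recorded.

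**The concern.** The charts are unblinded and retrospective: the clinician knew the drug and was free to record a cause or not. An on-treatment pneumonitis charted without a causal statement does not enter the result. Since no total is reported, a reader cannot tell how many such cases exist, or whether their share differs between cohorts.

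The cohorts differ in ways that could plausibly affect attribution. One drug is newer than the other. Controls can be indexed from January 2010, whereas palbociclib was first approved in February 2015. Protocol 9.7.3.4 concedes that the differing time periods may be a limitation. The SAP's list of amendments removes the analysis restricted to the post-approval period because too few controls were available, so no planned analysis compares the cohorts within one era.

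SAP section 1 says that the study is meant to support extending the indication to pre-/perimenopausal women, who were not in PALOMA-1 or PALOMA-2. With no rate, adjustment or total planned, two raw counts side by side are the only comparative safety information the study will produce.

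**Working it through.** **What the passages establish.** Protocol 9.7.3.6 and SAP 6.2 restrict the count to attributable cases. The variable tables make attribution an explicit chart statement. Protocol 9.8 rules out interpretation by the abstractor. No section plans a count of all documented cases, independent causality review, or a rule for unattributed cases. Protocol 9.9 mentions non-standard physician reporting and misclassification in general terms, but not this issue.

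**Plan's own figure.** There is none to reproduce. The documents give no expected incidence, attribution rate or precision for pneumonitis/ILD.

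**Inputs.** Cohort sizes are from SAP 5: "116 were treated with palbociclib plus AI, 80 were treated with AI monotherapy". Incidence and attribution probabilities are assumptions, varied over a range.

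**Formulas.**
- Expected reported cases = n × incidence × P(attribution written | case).
- Ratio of reported risks = (true risk ratio) × (ratio of attribution probabilities). At equal incidence, only the second factor remains.
- The probability that one cohort shows the higher reported proportion comes from exact binomial distributions with n = 116 and n = 80.

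**One case in full.** With 2% incidence in both cohorts and attribution of 80% (palbociclib + AI) versus 20% (AI alone):
- All cases: 116 × 0.02 = 2.32 versus 80 × 0.02 = 1.60.
- Reported: 2.32 × 0.80 = 1.86 versus 1.60 × 0.20 = 0.32.
- Ratio of reported risks: 0.80 / 0.20 = 4.0, against a true ratio of 1.0.

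**Range (all hypothetical, equal true incidence; palbociclib + AI listed first).**

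| Incidence | Attribution | All cases expected | Reported cases expected | Ratio of reported risks | P(palbociclib higher) | P(AI higher) | P(zero reported in AI) |
|---|---|---|---|---|---|---|---|
| 1% | 80% v 20% | 1.16 v 0.80 | 0.93 v 0.16 | 4.0 | 0.550 | 0.115 | 0.852 |
| 2% | 50% v 50% | 2.32 v 1.60 | 1.16 v 0.80 | 1.0 | 0.441 | 0.419 | 0.448 |
| 2% | 70% v 30% | 2.32 v 1.60 | 1.62 v 0.48 | 2.3 | 0.658 | 0.222 | 0.618 |
| 2% | 80% v 20% | 2.32 v 1.60 | 1.86 v 0.32 | 4.0 | 0.754 | 0.134 | 0.726 |
| 2% | 90% v 10% | 2.32 v 1.60 | 2.09 v 0.16 | 9.0 | 0.837 | 0.060 | 0.852 |
| 5% | 80% v 20% | 5.80 v 4.00 | 4.64 v 0.80 | 4.0 | 0.930 | 0.066 | 0.448 |

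A milder contrast, 80% versus 60%, gives 0.80 / 0.60 = 1.33. Reversing 70% and 30% gives 0.30 / 0.70 = 0.43, so the distortion can run either way. The 50% v 50% row shows no distortion of the ratio, but half the cases in each cohort go unreported.

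**Exposure time.** A count of all documented cases has its own difficulty if treatment durations differ. Protocol section 7 gives PALOMA-2 median progression-free survival of 24.8 versus 14.5 months. If treatment time followed that ratio (an assumption, and from a postmenopausal trial), equal monthly incidence would give about 24.8 / 14.5 = 1.7 times as many cases per patient on palbociclib. Attributed counts share this problem. A corrected result therefore needs person-time as well as n/N.

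**The case against.** The strongest reply is that the plan makes no comparative safety claim. It reports a number of cases per cohort, with no ratio, interval or test. Its single objective is response rate, SAP 4 rules out formal hypothesis testing, and Protocol section 7 says that the study is not a post-authorization safety study. A count described as attributable says what it is. Restricting it to attributed cases fits the no-interpretation rule and keeps out events with other causes, such as radiotherapy. This limits the weight of the point. It does not remove it, because the counts are still set out by cohort and the attributed cases can stay as a subset when the total is added.

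Three stronger readings are tempting, and the documents do not support them:
- **That attribution does differ between the cohorts, or that the count favours one of them.** Nothing in the documents shows how often clinicians attribute these events, by drug or by era. The ratios in the table simply return the assumed attribution probabilities.
- **That the expedited-reporting rule of Protocol 11 was adopted as the endpoint definition.** Neither Protocol 9.7.3.6 nor SAP 6.2 cites it. The shared term suggests it, but the variable tables alone establish the chart-attribution definition.
- **That the remedy is certainly one extra table row.** The Yes/No field is ambiguous: No may mean an unattributed event, or no attributed event. The tables list no onset date for this variable, although the existing window needs one. Data collection was due to end in 2Q2021, before the October 2021 SAP.

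**Conclusion.** The point holds as a limitation of the endpoint definition. As planned, the only safety result mixes incidence with attribution practice, across cohorts that differ in drug and calendar era, and leaves the reader no means of separating the two. Whether this creates, hides or leaves unchanged a difference between cohorts cannot be determined from the documents.

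The figures above show only what would follow if attribution differed. In the 2% scenarios the expected reported counts differ by fewer than two cases, yet with numbers this small that can decide which cohort looks worse, or whether the control cohort shows any case at all.

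The weight is moderate: the count is descriptive, secondary to response rate, and not part of a dedicated safety study. The correction is still worth making, because adding the total loses nothing that the plan now reports.

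**What to change.** In Protocol 9.7.3.6 and SAP 6.2:
- Report, by cohort, all provider-documented pneumonitis/ILD with onset during first-line treatment plus 30 days, regardless of attribution. Give n/N with exposure time. Treatment duration is derivable from the index start and end dates already collected.
- Show the explicitly attributed cases as a subset.
- Flag cases with pre-index ILD or pneumonitis and those with prior or concomitant radiotherapy, all of which are already collected.
- Define what No means in the Yes/No field, and add an event onset date.
- Leave explicit attribution as the criterion for the 24-hour reports in Protocol 11.

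**Cost.** If unattributed events and their dates were abstracted, the change is wording plus a few table rows. If only attributed events were recorded, a targeted re-query of the 196 charts for event and onset date is needed. The total will include some cases that the drug did not cause, which is why the subset and flags should appear beside it.

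**If the re-query cannot be done.** Label the result *clinician-attributed cases* and state in the limitations that it does not support an incidence comparison between the cohorts.
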